Cover Page for Clinical Trial Study

Official Title: The Effect of Animal-Assisted Therapy on Prosocial Behavior in Children with Developmental Delay or Autism Spectrum Disorder

NCT #: N/A

Date: November 11, 2024

Study Protocol

Clinical Study Description

The purpose of this study is to investigate the effect of animal-assisted therapy (AAT) on prosocial behavior and emotional regulation, both during and after AAT sessions, in children referred for an autism spectrum disorder (ASD) evaluation or documented developmental delay (DD) or behavioral concerns. We seek to address identified gaps in knowledge of the use of canines in therapy sessions by analyzing short- and long-term effects of AAT and human-animal interaction occurring in AAT sessions. Caregivers were given the option to enroll the child in the AAT study at the follow-up appointment after the diagnostic assessment was completed, or upon enrollment in the ASD program if the child had an ASD diagnosis. Each AAT study lasted between eight to 12 weeks, and caregivers had the option to re-enroll the child for the next study to continue addressing behavioral concerns. Animal-assisted therapy sessions lasted 30 to 45 minutes, depending on the age and ability of the participant. Sessions started with five to 10 minutes of free play with the canine, followed by sensory integration therapy based on the child's identified sensory profile. Participants then entered the clinic room for 20 to 30 minutes of a seated activity in which the therapist, a certified pediatric nurse practitioner (CPNP), taught coping and socialization strategies to participants and caregivers. Sessions concluded with five minutes of play with the canine. Play activities include fetch, soccer, hide and seek, and puzzles. The canine was trained to lay under the table in the clinic room while the therapist was working with the participants. He would provide grounding, light pressure, and deep pressure therapy if the participant became anxious during the sessions. The seated work was recorded using two cameras to ensure visibility of the interactions between the participant and therapist, canine, and caregiver; participant vocalizations and verbalizations; and participant facial expressions. We used two human-animal ethograms to code behavior during sessions and two behavioral assessments to note behavior occurring after sessions. All sessions occurred in the clinic located on the university's campus. Demographic data including participant age, gender, race, ethnicity, referral source, prior medical diagnoses, age of ASD or DD diagnosis, medications, and prior allied health, school, or psychological evaluations. The canine was trained as a therapy dog and was being trained as a service dog at the time of the study. The canine was present during sessions to interact with children and assist them to practice and develop skills to address identified deficits in social-emotional and adaptive functioning, prosocial behavior, and emotional regulation. AAT sessions were recorded to code interactions at a later time.

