Lastly, the Positive and Negative Affect Schedule (PANAS) was administered weekly to measure therapeutic effects occurring in everyday life outside of the AAT session. The PANAS is a 20-item questionnaire utilizing a 5-point Likert scale to assess positive and negative affect occurring the week prior to administration. Each domain has 10 items with scores ranging from 10 to 50, with lower scores reflecting lower levels of positive or negative affect and higher scores signifying higher positive or negative affect²⁹. Total scores on each scale are obtained by adding the scores for each item. Analysis of the PANAS demonstrates very good internal consistency reliability, with alphas ranging from 0.86 to 0.90 for Positive affect and from 0.84 to 0.87 for Negative affect.

Statistical Analysis Plan

This present study used standardized instruments to investigate human-animal interaction (HAI) occurring during AAT sessions and prosocial behavior and emotional regulation demonstrated by participants outside of AAT sessions. SPSS and Microsoft Excel were used to run the analysis. Descriptive statistics were utilized to compare prosocial behavior and emotional regulation occurring apart from AAT sessions between the two groups based on the self-report questionnaires completed by caregivers. A total of 144 sessions were conducted, 84 of which were recorded and coded to analyze HAI during sessions. Independent t-tests were used to analyze the differences in human-animal interaction among children with ASD with varying verbal abilities from the recorded sessions. The homogeneity of the variance (HOV) assumption between two groups was checked using Levene's test for equality of variances in SPSS program before conducting the t-tests analysis. Results of t-tests with adjusted degrees of freedom value were reported if the HOV was violated. The null hypothesis was set to reflect no significant difference in HAI between verbal and nonverbal groups for the independent t-tests; therefore, a significant difference in the human-animal interaction behaviors regarding the children's verbal abilities could be confirmed if the t-test results reject the null hypothesis. Cohen's d was used to report the effect sizes of the independent t-tests; values up to 0.20 were interpreted as small, 0.50 as medium, and 0.80 as large effect size.

Protocol Number: 2201382953
Investigator: [name]

Expiration Date: 03/31/2024
Last Approval Date: 04/01/2023

University of Arkansas System

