All interactions between the canine and participants will occur either at the A4A clinic, in the EPLEY Center for Healthcare Professionals, or at the Psychology lab on campus. The first interaction between the canine and the participant will focus on introducing the two and facilitating a bond through play, such as petting or brushing the canine, or throwing a ball. The Purdue University Veterinary College of Medicine O'HAIRE Coding System will be used to observe and code human behavior during this session. Drs. [name] and [name] use a variety of behavioral and developmental evaluations to identify concerns and provide strategies for home therapy to improve delays: 1. Participants ages 8 years and older who are cognitively capable will be asked to self-report their emotional state before and after each AAT session using an 11-point Likert scale chart in the shape of a thermometer, with ranges from "no distress/totally relaxed" to "highest anxiety/stress that you've ever felt." 2. Strengths and Difficulties Questionnaire 3. Positive and Negative Affect Schedule 4. Ages and Stages Questionnaire- 3rd edition 5. Ages and Stages Questionnaire: Social and Emotional - 2nd edition 6. Social-Emotional Assessment Measure 7. Vineland- 3rd edition 8. Social Responsiveness Scale- 2nd edition 9. PEDS: DM-AL 10. Stanford-Binet Intelligence Quota Test Caregiver satisfaction and perspectives of AAT integration in therapy sessions will be assessed via surveys. Demographic data including participant age, gender, race/ethnicity, referral source, prior medical diagnoses, age of ASD or DD diagnosis, medications, and prior allied health or psychological therapies will be collected on all participants. [name] will incorporate AAT into the therapy sessions at the A4A clinic that are guided by the Ages and Stages developmental and social/emotional assessments to target gross and fine motor skill, language, social, and emotional development. Parents will be given handouts that are designed to address deficits identified by the ASQ-3, ASQ:SE-2, and SEAM assessments. The canine will be present to interact with children as they are learning their skill for that week. For example, the canine will interact with the participant while the participant is learning a new skill, such as improvement in handwriting, and the participant will be able to interact and play with the canine if the participant focuses on completing the therapy assignment. Likewise, participants will earn points if they perform their therapy strategies at home and can use those points to interact and play with the canine at their next therapy session. Plush dog toys who look like the canine will be given to pediatric participants as incentive to perform their home therapies. The following data will be collected on the canine: 1. The Canine Behavioral Assessment and Research Questionnaire (C-BARQ), a validated measure to quantify animal behavior during training developed by the University of Pennsylvania in 2003. The C-BARQ database will be used to compare the canine's training progress with other Black Labrador Retriever dogs and can also alert to the onset of behavioral problems so [name] can target these concerns early in the training process. 2. The canine behavior ethogram which assesses 26 canine behaviors during human-animal interactions. The ethogram is divided into three categories: affiliative indicators, moderate stress indicators, and high-stress indicators. The research team will track the number of AAT sessions in which the canine participates each day to assess for variations in temperament and performance. 3. The exact minutes in which canine behaviors are present will be recorded in each AAT session, noting patterns that indicate fatigue or distress. Human-animal interaction will be assessed by: 1. The Purdue University Veterinary College of Medicine O'HAIRE Coding System will be used to observe and code human behavior during AAT sessions. Observable behaviors categories captured by the OHAIRE Coding System include Interactive Behaviors (Social Communication & Environmental Interaction), Emotional Display (Facial, Verbal), and Interfering Behaviors (Aggression, Overactivity, Isolation). The OHAIRE-V3 assessment will be used to calculate a human-animal bond score to quantify the interactions taking place between the pediatric participants and the animal. The ELAN Coding software will be used to achieve high inter-rater reliability through precise timing of observed interactions. All AAT sessions will be recorded after receiving consent from families to retroactively code participant behavior during sessions.

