[name]'s lab computers within 24 hours and then immediately deleted from the camcorder device. Video files will be stored on a password-protected computer as password-protected documents.

- **Minimal Risk is defined as risks of harm not greater than those ordinarily encountered in daily life or during the performance of routine physical or psychological examinations or tests. Will participants be exposed to more than minimal risk? Include in your consideration the potential of mental risks if asking sensitive questions, or legal or reputational risks in case of breach of confidentiality.**

Yes

- **Describe the risks in question and any precautions that will be taken to minimize those risks.**

Participants will not be exposed to more than minimal risks while receiving developmental or behavioral evaluations. Participants will be exposed to the canine during therapy sessions for approximately 10 to 15 minutes weekly. The canine will be removed if signs of fatigue, fright, or irritation appear. He will remain on leash throughout the entire AAT session and will be wearing a harness. Honors students will have the canine's leash during the AAT session and will hold him by the harness handle. Also, [name] will assess the disposition of the pediatric participants before allowing the canine to come to the room and will not allow the canine to participate if the pediatric participant's behavior is disruptive or potentially dangerous for the canine.

- **Are there any direct benefits to the participants for participating in this study?**

Yes

- **Describe the benefits participants will or may receive.**

Pediatric participants will receive one plush toy that looks like the canine they are working with.

- **Will the proposed research involve deception or the withholding of information from participants?**

No

- **Will the proposed research necessitate medical clearance from a physician prior to participation?**

No

- **Will the proposed research involve gathering biological samples (blood, tissue, etc.)?**

No

- **Will the proposed research involve administering of substances or providing food and drink, other than water, to participants?**

No

- **Will the proposed research involve physical exercise or conditioning?**

No

- **Does the research require review by a non-UofA IRB?**

No

- **Does this research require approval from another institution or agency, such as a school or privately owned business?**

No

Protocol Number: 2201382953

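### The verbal versus nonverbal t-tests use 84 of 144 sessions, with no account of how these were captured and no term for session position, so verbal ability cannot be separated from which sessions were coded.

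*Combined protocol and SAP*

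**What the plan says.** The Statistical Analysis Plan gives the coverage: "A total of 144 sessions were conducted, 84 of which were recorded and coded to analyze HAI during sessions". It gives the analysis as: "Independent t-tests were used to analyze the differences in human-animal interaction among children with ASD with varying verbal abilities from the recorded sessions". It describes Levene's test and Cohen's d, but no covariate, no handling of uncoded sessions and no sensitivity analysis.

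The IRB application (Human Subjects Protocol Interview) states the recording plan twice, in the answers on procedures and on data collection: "All AAT sessions will be recorded after receiving consent from families to retroactively code participant behavior during sessions".

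Three other statements bear on whether one session can stand in for another:

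- Clinical Study Description: "Each AAT study lasted between eight to 12 weeks, and caregivers had the option to re-enroll the child for the next study". Children can therefore differ in how many sessions they have had with the dog.
- IRB application, procedures: "The first interaction between the canine and the participant will focus on introducing the two and facilitating a bond through play". OHAIRE coding is planned for that session.
- IRB application, risks: the clinician "will not allow the canine to participate if the pediatric participant's behavior is disruptive" or could endanger the dog.

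**The concern.** Objective 1 asks whether interaction with the dog differs by verbal ability, and the answer rests on the coded sessions alone. The documents do not say why 60 sessions have no coded data, how the 84 divide by verbal group, child, week or enrolment cycle, or whether the t-test compares sessions, video segments or child means.

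Two routes could turn selective capture into an apparent group difference.

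- **Timing.** Interaction may change as a child gets to know the dog. If one group's coded sessions come from a different part of the programme, the comparison mixes verbal ability with exposure.
- **Behaviour.** If the dog is kept out when a child is disruptive, whether there is interaction to code depends on the behaviour under study, and this may happen more in one group.

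A two-sample t-test has no term for either. Averaging per child first would not help, because the averages would still come from whichever weeks were captured.

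**Working it through.** **Inputs from the documents.** 144 sessions conducted and 84 recorded and coded (Statistical Analysis Plan); cycles of 8 to 12 weeks (Clinical Study Description); bond score of 0 to 36 per one-minute segment (Methods); Cohen's d read as "values up to 0.20 were interpreted as small, 0.50 as medium, and 0.80 as large effect size" (Statistical Analysis Plan). The plan prints no percentage, alpha, power or sample-size calculation, so there is no design figure to reproduce.

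**Step 1, coverage.** 84/144 = 58.3% coded. 144 − 84 = 60, and 60/144 = 41.7% not coded.

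**Step 2, formula.** Let a group have coded share p and let δ be its coded mean minus its uncoded mean. The mean over all its sessions is p × coded + (1 − p) × uncoded, so using coded sessions alone shifts the group mean by (1 − p) × δ. For groups A and B the bias in the difference is

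(1 − pA) × δA − (1 − pB) × δB.

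**Step 3, unequal coding with the same δ in both groups.** The split by group is unknown. Assume 72 sessions per group and δ of 2, 4 or 6 points.

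| Coded, A v B | Coded share | Difference in uncoded share | Size of bias for δ = 2, 4, 6 |
|---|---|---|---|
| 42 v 42 | 58% v 58% | 0 | 0, 0, 0 |
| 50 v 34 | 69% v 47% | 16/72 = 0.222 | 0.4, 0.9, 1.3 |
| 54 v 30 | 75% v 42% | 24/72 = 0.333 | 0.7, 1.3, 2.0 |
| 60 v 24 | 83% v 33% | 36/72 = 0.500 | 1.0, 2.0, 3.0 |

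**Step 4, δ differing between groups.** Equal coding rates do not guarantee zero bias. With 58.3% coded in both groups and δ of 4 and 0, the bias is 0.417 × 4 − 0.417 × 0 = 1.67 points. Nor do unequal rates guarantee bias: with 75% and 42% coded and δ of 4.67 and 2, it is 0.25 × 4.67 − 0.583 × 2 = 0. On the plan's effect-size scale, at equal coding a spurious d of 0.20 needs δ to differ between groups by 0.20/0.417 = 0.48 SD, and a spurious d of 0.50 needs 0.50/0.417 = 1.20 SD.

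**Step 5, timing alone.** Suppose one group is captured as early as possible and the other as late as possible, each at 58.3%. Their mean weeks then differ by L × (1 − 84/144): 8 × 0.417 = 3.3 weeks, or 12 × 0.417 = 5.0 weeks. Multiplying by an assumed linear trend gives a spurious d. The rejection rate with no true difference is Φ(d/√(2/42) − 1.96) + Φ(−d/√(2/42) − 1.96), assuming 42 v 42 independent sessions, SD 1 and two-sided 0.05.

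| Trend (SD per week) | 8 weeks: d, rejection | 12 weeks: d, rejection |
|---|---|---|
| 0.02 | 0.07, 6% | 0.10, 7% |
| 0.05 | 0.17, 12% | 0.25, 21% |
| 0.10 | 0.33, 33% | 0.50, 63% |

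This is the extreme arrangement. With half the imbalance the rates run from 5% to 12% over 8 weeks and from 6% to 21% over 12 weeks.

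**The case against.** The strongest reply is that little of the mechanism is stated in the documents, and several stronger readings fail.

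- **That the recording plan was breached.** A reader might infer this from 84 against 144. Recording was conditional on family consent, and the SAP wording does not separate sessions never filmed from sessions filmed but not coded. Only unfilmed sessions of consenting families would be a departure. Refusals, however, could remove whole children and still be selective.
- **That interaction changes over the programme.** No section says so. The introductory bonding session comes from the prospective IRB application. The Clinical Study Description, written after the fact, gives a single session structure that opens and closes with play, and says the seated work was filmed. The Methods section describes continuous filming of unstructured interaction instead. If only seated work was coded, an introductory play session may matter little.
- **That sessions were pooled regardless of week.** This is inferred from the absence of a time term, because the unit of analysis is not given.
- **That the dog's continuing service training adds to the bias.** The dog was already a trained therapy dog, and nothing links its training to verbal group or to recording.
- **That the 84 are presented as standing for all 144.** The plan discloses both counts and ties the t-tests to the recorded sessions.

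These points stand and limit the claim. They do not supply the missing reasons or breakdown, and they do not give the t-test a way to allow for session position.

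**Conclusion.** The point holds as a weakness in the method with a cheap improvement available. The stated analysis for Objective 1 cannot separate verbal ability from which sessions were captured. The group difference is biased if capture or its timing differs by verbal group and interaction changes with exposure, or if missingness depends on behaviour, unless the effects happen to cancel.

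A reader might infer that the reported comparison is biased, or that equal coding rates would clear it. The documents support neither. Size and direction cannot be determined from them, and Step 4 shows that equal rates are not enough. The 0.7 to 2.0 points rest on an assumed 72/72 split, 54 v 30 coded and a common contrast of 2 to 6 points. The timing table rests on assumed trends, independent sessions and the most extreme capture pattern.

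**What to change.** 1. For Objective 1, replace the unadjusted t-test with a model of the coded sessions that includes verbal group and cumulative session number with the dog, counted across re-enrolments, and that accounts for repeated sessions per child, for example with a child random effect.
2. Add a sensitivity analysis limited to session numbers coded in both groups. Add another without the first session, if an introductory session was held and coded.
3. Support these with a table of conducted, recorded and coded sessions by verbal group, child and session number, with the reason for each gap: no consent, not filmed, or filmed but not coded.
4. Limit the conclusion to coded sessions. The adjustment deals with session position and does not remove behaviour-dependent missingness.

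The cost is one table, a modest change of model and SAP wording. It needs no new data, provided that dates were kept for all 144 sessions, which the documents do not confirm. The downside is some loss of precision where the groups' session numbers do not overlap, and a narrower claim.

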
The 3-AAT Observation ethogram, adapted with permission from Johns Hopkins University, was used to code both canine and human interaction during AAT sessions. The revised ethogram appraises the frequency of six domains of human interaction (affection, play, care, communication, comfort, withdrawal) and 24 subdomains of human behavior that can occur in an AAT session as seen in Table 1. The ethogram assesses the frequency, intensity, and duration of the interactions between the canine and child. Frequency is measured by a tally count and duration is assessed by rounding either up or down to the nearest 30 second mark. Each interaction has a code for intensity from 0 (not intense) to 3 (the most intense), and the mode of the interaction was entered to run the analysis.

The Strengths and Difficulties Questionnaire (SDQ) is a 25-item tool developed to assess five domains: Emotional Problems, Conduct Problems, Hyperactivity, Peer Problems, and Prosocial. The SDQ is the most used instrument in measuring therapeutic effect of interventions within the emotional state in children and adolescents ages 2 to 18 years, demonstrating reliable internal consistency and validity. The SDQ has two versions, one to be administered at the initiation of therapy and then a follow-up version that includes two additional questions examining the impact of the therapeutic intervention. Scores from four behavioral domains range from zero ("normal") to 10 ("very high concerns"), while Prosocial domain scores are reversed so that 10 indicates "normal" behavior and zero signifies "very high concerns". The SDQ also assesses the total, impact, internalizing, and externalizing scores to provide a complete overview of the child's behavior during the past four weeks. Total scores are the sum of the behavior domains except the Prosocial domains and range from zero (normal) to 40 (very high). Impact scores range from zero (normal) to 10 (very high) and reflect overall distress and impairment interfering with daily social interactions. Internalizing scores reflect the Emotional Problems and Peer Problems domains, while Externalizing scores are the sum of the Conduct Problems and Hyperactivity domains. Both the Internalizing and Externalizing domain scores range from zero (normal) to 20 (very high). The initial SDQ was administered at the beginning of the study and the follow-up assessment was used subsequently every four weeks until the study concluded.

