
- **How long are the procedures likely to take? Include duration and frequency.**

The A4A weekly therapy sessions will last about 30 minutes; however only it is expected that the total HAI time will be approximately 10-15 minutes, depending on the therapy activity. Honors students will assist the canine with [name] during the sessions and will take the canine to [name] office once the HAI part of the appointment has ended.

- **How will information be given to people to get their informed consent to participate in this research? Answers should include specific methods (e.g., verbal consent, information handout, online consent form, full consent form requiring signature documentation.) **Please note that consent materials -- from a script for verbal consent to full consent forms that require participant signature -- must be uploaded in the Notes and Attachments section.**

[name] will contact parents/guardians of potential participants to explain the AAT program and gauge their interest. If interested, parents will come to the A4A clinic on the first floor of ECHP to meet the canine and sign the informed consent form. Verbal assent will be obtained from pediatric patients who are cognitively able to give it.

- **Does data collection rely on a scheduled event, such as a convention or specific date?**

No

- **How will your data be collected? Include all that apply: online, on paper/in person, audio and/or video recordings. **Please note that all data collection materials will need to be uploaded in the Notes and Attachments section. This includes: surveys, questionnaires, interview questions or anything that is given to or asked of a participant.**

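### Independent t-tests on 84 coded sessions ignore repeated sessions from the same child; with the session as unit, the verbal-versus-nonverbal p-values are too small

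*Combined protocol and SAP*

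**What the plan says.** The Statistical Analysis Plan gives its sample size in sessions: "A total of 144 sessions were conducted, 84 of which were recorded and coded to analyze HAI during sessions". The next sentence names the test: "Independent t-tests were used to analyze the differences in human-animal interaction among children with ASD with varying verbal abilities from the recorded sessions". The Design section repeats that sentence. The null hypothesis is "no significant difference in HAI between verbal and nonverbal groups for the independent t-tests", and a difference "could be confirmed if the t-test results reject the null hypothesis".

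The one adjustment described follows Levene's test: "Results of t-tests with adjusted degrees of freedom value were reported if the HOV was violated".

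On how often a child is seen, the Clinical Study Description says: "Each AAT study lasted between eight to 12 weeks, and caregivers had the option to re-enroll the child for the next study". The duration question in the Human Subjects Protocol Interview says: "The A4A weekly therapy sessions will last about 30 minutes". The Subjects table of the IRB record lists 20 children.

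On aggregation, the Methods section says of the ethogram's intensity codes that "the mode of the interaction was entered to run the analysis", without saying whether that is one mode per session or per child. It scores the OHAIRE bond measure per 1-minute segment and describes no reduction to one value per child.

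**The concern.** An independent-samples t-test requires every observation to be independent of the others. Verbal versus nonverbal is a contrast between children, so the independent unit is the child. Several sessions from one child share that child's temperament, ability and relationship with the dog, and they cannot count as separate evidence about the group difference. The unequal-variance adjustment does not help, because it still treats each session as independent.

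The t-test is the only inferential method in the plan; behaviour outside sessions is compared descriptively. If its standard error is wrong, every significant group difference the study reports is affected. Cohen's d would be nearly unbiased, but any interval around it would be too narrow.

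**Working it through.** The documents give no power calculation, alpha or p-value, so there is no figure of the plan's own to reproduce.

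**Inputs from the documents**
- Coded sessions: 84 of 144 (Statistical Analysis Plan).
- Children: 20 (IRB record, Subjects table).
- Schedule: weekly sessions, courses of 8 to 12 weeks, re-enrolment allowed.

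**Assumptions**
- Two-sided alpha of 0.05, and all 84 coded sessions enter the test.
- Number of children analysed, *k*: 20, 12 or 8.
- ICC: 0.05 to 0.7.
- Unless stated otherwise: even spread of sessions, equal groups, normal outcomes.

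**Step 1: repeats, with no ICC needed.** With at most 20 children, 84 − 20 = 64 sessions are repeats, and 64/84 = 76%. The average is 84/20 = 4.2 coded sessions per child. Full independence would need 84 different children, 4.2 times the listed count. The schedule agrees: 144/12 = 12 and 144/8 = 18, so 144 sessions amount to only 12 to 18 full courses.

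**Step 2: size of the error if the session is the unit.** The design effect is DE = 1 + (84/*k* − 1) × ICC, and the effective sample size is 84/DE. The approximate type I error is 2 × [1 − Φ(1.96/√DE)]. For example, with *k* = 20 and ICC 0.3, DE = 1 + 3.2 × 0.3 = 1.96, the effective sample size is 84/1.96 = 42.9, and the error is 2 × [1 − Φ(1.40)] = 0.162. Simulation (20,000 runs per cell) checks the approximation:

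| *k* | ICC | DE | Effective N | Type I error, formula | Type I error, simulated |
|---|---|---|---|---|---|
| 20 | 0.05 | 1.16 | 72.4 | 0.069 | 0.070 |
| 20 | 0.1 | 1.32 | 63.6 | 0.088 | 0.091 |
| 20 | 0.3 | 1.96 | 42.9 | 0.162 | 0.170 |
| 20 | 0.5 | 2.60 | 32.3 | 0.224 | 0.236 |
| 20 | 0.7 | 3.24 | 25.9 | 0.276 | 0.297 |
| 12 | 0.05 | 1.30 | 64.6 | 0.086 | 0.088 |
| 12 | 0.1 | 1.60 | 52.5 | 0.121 | 0.128 |
| 12 | 0.3 | 2.80 | 30.0 | 0.241 | 0.246 |
| 12 | 0.5 | 4.00 | 21.0 | 0.327 | 0.343 |
| 12 | 0.7 | 5.20 | 16.2 | 0.390 | 0.425 |

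In the same cells, a t-test on one mean per child gives 0.050–0.053. With 8 children, which would imply re-enrolment (144/8 = 18 sessions each), the simulated session-level error is 0.16–0.52 for ICC 0.1–0.7. Welch's test on child means gives 0.035–0.052 across 8 to 20 children.

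**Step 3: sensitivity (ICC 0.1–0.7).** An uneven spread of sessions raises the error to 0.12–0.40 (20 children) and 0.16–0.53 (12). A group split near 1:2 changes little: 0.09–0.30 and 0.13–0.42.

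**Step 4: what a reported p-value would mean.** Divide the session-level critical value (82 df) by √DE and refer it to *k* − 2 df. A session-level p of 0.05 then corresponds to about 0.10, 0.17 and 0.23 with 20 children, and 0.15, 0.26 and 0.34 with 12 (ICC 0.1, 0.3, 0.5).

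**Step 5: precision of Cohen's d.** With a true d of 0.50 and ICC 0.1–0.7, the mean estimate is 0.50–0.54. A session-level 95% interval of about ±0.44 covers the truth only 91–71% of the time with 20 children and 88–58% with 12.

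**The case against.** The strongest reply is that the plan never names the session as the unit. The test sentence speaks of children, the null hypothesis concerns groups of children, and the reference to recorded sessions may only identify the data source. The ethogram mode shows that some aggregation came before testing. If each child contributed one value, the inflation falls away and only a reporting gap remains. This stands as a condition on the conclusion. It does not rescue the plan: no reduction to one value per child is described for either instrument, and the only count given is of sessions. If the 1-minute OHAIRE segment was the unit, the dependence would be worse.

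The 20 children are a planned count in an IRB application, not the number analysed. That is true, and the 76% depends on it. Weekly sessions over 8 to 12 weeks make repeats near-certain in any case.

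The magnitudes rest on assumed ICCs and normal outcomes, whereas the ethogram yields tallies, rounded durations and 0–3 modes. This is also fair. At an ICC of 0.05 the error is only 7–9%. A simulated skewed 0–3 outcome, with assumed cut-points, gives somewhat lower inflation: 7–27% with 20 children and 10–39% with 12. The direction does not change.

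**Conclusion.** The concern holds and needs correction. The plan omits the unit of analysis, the number of children per group and any handling of repeats; that much is certain. Read naturally, it applies a test for independent observations to clustered sessions, and its p-values are too small at any positive ICC. For ICC 0.05–0.7 with even spread and equal groups, the actual error of a nominal 5% test is about 7–30% with 20 children and 9–42% with 12. The exact size cannot be fixed, because the ICC, the number of children analysed, their spread and the group split are not in the documents. If child-level summaries were used, the p-values are not inflated for this reason, but a reader cannot establish that from the plan.

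**What to change.** State the unit of analysis and make it the child, by one of two routes:

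- **Child means.** Average each child's coded sessions over all enrolments and apply Welch's t-test. This is the simpler default, and its error rate was checked above. Averaging the 0–3 intensity modes needs a short justification.
- **Mixed model.** Fit all coded sessions with verbal group as a fixed effect, one child random intercept spanning re-enrolments, and Satterthwaite or Kenward-Roger degrees of freedom. This route was not simulated here, and a linear model should be justified for tallies and 0–3 scores.

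Under either route, keep one identifier per child across enrolments and state how a child whose verbal group changes is classified. Report unique children and coded sessions per group beside each p-value. Standardise Cohen's d by the total (between- plus within-child) SD, name that SD, and give an interval that allows for clustering. If child means were in fact analysed, one sentence and the number of children per group are enough.

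The cost is SAP wording and a re-run on data already coded, in software already used. Intervals will widen and fewer results will be significant. For a true d of 0.50 and ICC 0.1–0.7, power on child means is 47–22% with 20 children and 35–14% with 12, against an apparent 58–61% at session level. That apparent power is not real, because it comes from a test with an inflated error rate.
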